physiotherapist and the family under the control of the physiotherapist. Family-centered physiotherapy practices have come to the fore in recent years, and are a treatment approach applied by the family that focuses on the environment and what the child can do. Motor reactions are activated by providing normal sensory input. Telerehabilitation is the provision of rehabilitation services by rehabilitation specialists with computer-based technologies and communication tools. It is a developing method that provides rehabilitation services by reducing time, distance and cost barriers and using technological tools. There are previously studies on a portable smart system that is monitored remotely and created for early assessment and intervention.

Although the importance of early physiotherapy approaches is known today, when the literature is examined, it is seen that the number of studies is insufficient and there is no consensus yet on which therapy approach is more successful. No previous study has been found in which family education of risky babies was followed up with telerehabilitation.

2. Objectives

Primary Objective

Evaluate the effectiveness of family-centered, goal-directed early physiotherapy approaches in high-risk infants using telerehabilitation.

Secondary Objectives

- 1. Compare the motor, cognitive, and language developmental progress of infants in telerehabilitation and single-session education groups.
- 2. Assess family satisfaction with telerehabilitation-based physiotherapy.
- 3. Measure neurological outcomes using Hammersmith Infant Neurological Examination (HINE).
- 4. Determine the achievement of individualized treatment goals using the Goal Attainment Scale (GAS).

3. Study Design

Type of Study

A prospective, randomized, controlled trial conducted at the Risky Infants Polyclinic.

Duration

12 weeks, with evaluations conducted at baseline, 4th, 8th, and 12th weeks.

Groups

- 1. **Telerehabilitation-Based Group**: Families received exercise training in the clinic, followed by weekly real-time video-conference sessions (1 day/week) and follow-up phone calls (2 days/week).
- 2. **Single-Session Education Group**: Families received a single session of exercise training in the clinic and were asked to continue the exercises independently.

4. Participants

Inclusion Criteria

- Premature infants (<37 weeks) treated in neonatal intensive care units.

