- Infants with neurological abnormalities (muscle hypertonia, hypotonia, overstimulation, abnormal general movements, or cranial ultrasound abnormalities).
- Infants aged 0-12 months (corrected age for prematurity applied).
- Diagnosed as at-risk for motor or developmental delay.
- Infants whose medical treatments are complete and are no longer in neonatal intensive care.
- Families who agree to participate and provide informed consent.

Exclusion Criteria

- Infants with congenital cyanotic heart disease, cystic fibrosis, genetic diseases, or congenital anomalies.
- Infants on ventilators.
- Families unable to attend regular check-ups or weekly communication.
- Infants already enrolled in special education or rehabilitation centers.

5. Outcome Measures

Primary Outcomes

- 1. Changes in neuromotor development using the Hammersmith Infant Neurological Examination (HINE).
- 2. Cognitive, motor, and language development using Bayley III.
- 3. Goal achievement using the Goal Attainment Scale (GAS).

Secondary Outcome

4. Family satisfaction using a custom Satisfaction Survey.

6. Intervention

Training Protocol

- Exercises tailored to neuromotor developmental stages, delivered by experienced pediatric physiotherapists.
- Families instructed to perform exercises for 30-45 minutes, 3 days per week, for 12 weeks.
- Telerehabilitation group received one supervised video-conference session weekly, with phone call follow-ups for the remaining two days.
- Single-session group received instructions during one in-clinic session with no additional follow-up.

7. Data Collection and Tools

Demographics

• Collected using forms capturing infant and family data (age, education, marital status, economic status, number of children, etc.).

Developmental Assessments

- 1. **Bayley III**: Evaluates cognitive, motor, and language development.
- 2. **HINE**: Assesses cranial nerve function, posture, tone, reflexes, and orientation.
- 3. GAS: Tracks individualized treatment goal achievement.

Satisfaction Survey

Assesses family satisfaction with treatment.

8. Statistical Analysis Plan (SAP)

Sample Size Calculation

- Based on a similar study (Pineda et al., 2020), the effect size was calculated as 1.09.
- Using G*Power 3.1.9.2, a total sample size of 24 infants (12 per group) was determined for α =0.05 and power=0.95.

Statistical Methods

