• **Descriptive Statistics**: Mean, standard deviation, minimum, and maximum values for quantitative data; frequency and percentage for qualitative data.

• Group Comparisons:

- Mann-Whitney U and chi-square tests for continuous and categorical demographic data.
- Wilcoxon Signed-Ranks Test for pre- and post-treatment comparisons of Bayley III, HINE, and GAS scores.
- **Significance Level**: p<0.05.

9. Ethical Considerations

- The study received ethical approval from the relevant institutional review board.
- Signed informed consent obtained from all participating families.
- Data confidentiality and anonymity maintained throughout the study.

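### Section 8 names no between-arm test for HINE, Bayley III or GAS and no adjustment for the infant's own baseline score; a baseline-adjusted comparison would supply both at almost no cost

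*Combined protocol and SAP*

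**What the plan says.** Section 5 (Primary Outcomes) lists "Changes in neuromotor development using the Hammersmith Infant Neurological Examination (HINE" first and "Cognitive, motor, and language development using Bayley III" second; GAS is third. Only HINE is worded as change, and no time point or between-arm contrast is given for any of the three.

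Section 3 describes a randomized controlled trial lasting "12 weeks, with evaluations conducted at baseline, 4th, 8th, and 12th weeks", so each infant is assessed before treatment starts. Secondary Objective 1 in Section 2 is to "Compare the motor, cognitive, and language developmental progress of infants in telerehabilitation and single-session education groups".

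Section 8 (Statistical Methods) gives two lines of tests under group comparisons: "Mann-Whitney U and chi-square tests for continuous and categorical demographic data" and "Wilcoxon Signed-Ranks Test for pre- and post-treatment comparisons of Bayley III, HINE, and GAS scores". No regression, ANCOVA, mixed model or covariate appears. On sample size, Section 8 says that "the effect size was calculated as 1.09" and that "a total sample size of 24 infants (12 per group) was determined for α =0.05 and power=0.95". It does not say in what units, or for which outcome, the 1.09 was derived.

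**The concern.** A signed-ranks test of pre against post asks whether infants within a group changed. It does not ask whether one group changed more than the other, and infants can be expected to develop over 12 weeks in either arm. The comparison that the trial was randomized to make therefore has no named test.

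Whoever adds that test will find an outcome called change and an analysis built on pre/post differences, so comparing change scores between arms is the likely default. Subtracting baseline fixes the slope of week-12 score on baseline score at 1. With equal SDs the true slope is rho. When rho is below 1, subtraction over-corrects: an arm that starts lower by chance tends to show the larger gain. When rho is below 0.5, the change score is noisier than the week-12 score alone. With 12 infants per arm, both the lost precision and the chance imbalance can be material.

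**Working it through.** **Inputs from the documents.** 12 infants per arm; effect size 1.09; alpha 0.05; power 0.95 (all Section 8); assessments at baseline and weeks 4, 8 and 12 (Section 3).

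**Assumptions.** The documents give no SD and no correlation. I take equal SDs at baseline and week 12, and a correlation rho of 0.3, 0.5 and 0.7, with higher values shown where they change the conclusion.

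**1. The plan's own figure.** Read as a two-sided two-sample t test, d = 1.09 at alpha 0.05 and power 0.95 needs 23 per arm (46 in total); one-sided it needs 19 per arm (38). At 12 per arm the power is 0.72 two-sided and 0.83 one-sided. Of the tests tried, 12 per group matches only a one-sided within-group signed-ranks test with 1.09 as a paired effect size (power 0.96). The stated 24 therefore does not reproduce as a between-arm calculation, and any between-arm analysis starts short of power.

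**2. Variance of the arm difference**, in units where the week-12 score alone has value 1:
- change score: 2(1-rho)
- week-12 score alone: 1
- week-12 score adjusted for baseline: 1-rho²

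Adjusted against change: (1-rho²)/(2(1-rho)) = (1+rho)/2, a saving of (1-rho)/2. Adjusted against week-12 alone: a saving of rho².

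**3. Cost of estimating the slope.** With normally distributed baselines and N = 24, the adjusted variance is multiplied on average by 1 + 1/(N-4) = 1 + 1/20 = 1.05. The realised saving against change is then 1 - 1.05(1+rho)/2. Simulation at 12 per arm (20,000 trials) gave 32%, 20% and 11% at rho 0.3, 0.5 and 0.7.

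| rho | saving vs change, large sample | same, slope estimated (closed form) | saving vs week-12 alone, large sample |
|---|---|---|---|
| 0.3 | 35% | 1 - 1.05×0.65 = 32% | 9% |
| 0.5 | 25% | 1 - 1.05×0.75 = 21% | 25% |
| 0.7 | 15% | 1 - 1.05×0.85 = 11% | 49% |
| 0.9 | 5% | 1 - 1.05×0.95 = 0.3% | 81% |

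Against change, break-even is at rho = 2/1.05 - 1 = 0.905. At rho 0.95 adjustment costs about 2% (1 - 1.05×0.975 = -2.4%).

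**4. Chance imbalance.** The arm difference in change correlates with the arm difference at baseline at -√((1-rho)/2): -0.59, -0.50 and -0.39 at rho 0.3, 0.5 and 0.7.

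**5. Power at 12 per arm**, two-sided 0.05, simulated with the slope estimated. The answer depends on what 1.09 is a multiple of:

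| rho | 1.09 in week-12 SDs: change → adjusted | 1.09 in change-score SDs: change → adjusted |
|---|---|---|
| 0.3 | 0.58 → 0.74 | 0.72 → 0.87 |
| 0.5 | 0.72 → 0.82 | 0.72 → 0.82 |
| 0.7 | 0.91 → 0.93 | 0.72 → 0.77 |

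Type I error was about 0.05 for both analyses. No adjusted entry reaches 0.95.

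**The case against.** The strongest reply is that the plan contains no between-arm change-score test, so no planned estimate exists whose variance is being wasted. That is right. A reader might infer from the HINE wording that the trial will discard 15-35% of its information. The documents do not support that: the range compares baseline adjustment with an analysis that the SAP never specifies, and it rests on an assumed rho. The wording itself is also loose; it may be ordinary language for development over time rather than a defined subtraction. Bayley III and GAS are not worded as change at all, and if week-12 Bayley scores were compared the relevant saving would be rho², not (1-rho)/2.

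The range could also be too favourable. Infants are enrolled from 0 to 12 months of corrected age (Section 4). If raw scores depend strongly on age, rho could be high and the gain over change would almost vanish.

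Finally, a reader might infer that a change-score comparison would be biased. It would not: under randomization it is unbiased with correct type I error, and its standard error already reflects chance baseline differences.

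All of this limits the size and kind of the claim. It does not supply the missing between-arm test, nor give a reason to leave a measured baseline out of it. The Mann-Whitney line could be stretched to cover continuous outcomes, but as written it is for demographic data, and it would still use no baseline covariate.

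**Conclusion.** The point holds in a conditional form. It is a fact of the text that Section 8 names only a within-infant test for HINE, Bayley III and GAS, with no between-arm outcome test and no baseline adjustment. The missing contrast is the larger gap; the form it should take is the second.

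If arms were compared on change, adjustment would save (1-rho)/2 of the variance: 15-35% for rho 0.3-0.7, about 11-32% with the slope estimated in 24 infants, and close to nil at rho 0.9. If week-12 scores alone were compared, it would save about rho² before the same small-sample cost. These figures assume equal SDs and a correlation that the documents do not give.

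What is at stake beyond the missing test is precision and sensitivity to chance imbalance, not validity. The size of the power gain cannot be fixed while the units of 1.09 are unstated, and under neither reading does adjustment restore 0.95 at rho 0.3-0.7. The sponsor should make this change, but it does not cure the sample size.

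**What to change.** In Section 8, state that the primary between-arm comparison of week-12 HINE, and of each Bayley III score, is a linear model for the week-12 score with arm and the infant's own baseline score on the same scale. Report the adjusted arm difference with its confidence interval. If a rank method is preferred, in keeping with the rest of the SAP, use Quade rank ANCOVA with the same baseline score. Keep the within-arm Wilcoxon tests as descriptive only. In Section 5, name the week-12 HINE score as the outcome so that it matches.

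GAS also needs a named between-arm test. The documents do not describe how it is scored at baseline, so I do not propose baseline adjustment for it here.

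The cost is SAP wording and one model degree of freedom (22 to 21 residual). The scheduled assessments already provide the data.

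### Three to five primary scores at p<0.05, with no between-arm test, success rule or multiplicity adjustment, leave the false-positive rate of the primary conclusion undefined

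*Combined protocol and SAP*

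**What the plan says.** Section 5 (Outcome Measures) numbers three primary outcomes without ranking them: HINE, Bayley III and GAS. The Bayley III item reads "Cognitive, motor, and language development using Bayley III". Counting instruments gives three primary scores; counting Bayley domains separately gives five.

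Section 8 (Statistical Methods) gives these scores one analysis: "Wilcoxon Signed-Ranks Test for pre- and post-treatment comparisons of Bayley III, HINE, and GAS scores". The tests that compare groups are assigned elsewhere: "Mann-Whitney U and chi-square tests for continuous and categorical demographic data". The threshold is a single line: "Significance Level: p<0.05". No section gives a testing order, an adjustment, a primary time point, or a statement of whether one, some or all scores must be positive.

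The sample size in Section 8 rests on one figure, "the effect size was calculated as 1.09", from which "a total sample size of 24 infants (12 per group) was determined". It does not say which score that figure describes. Section 3 schedules assessments at baseline and weeks 4, 8 and 12. Section 2 lists the between-group comparison of development, HINE and GAS under secondary objectives, although Section 5 makes the same measures primary.

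**The concern.** The trial is randomized and its purpose is comparative, so its primary conclusion should be a statement about telerehabilitation against single-session education. The plan does not say which test supports that statement, or which pattern of results across three to five scores would justify it. Once a between-arm test is supplied, any score that happens to reach p<0.05 could be presented as the positive primary result without departing from the plan.

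Adjusting the Wilcoxon tests would not solve this. They ask whether infants change within an arm over 12 weeks, not whether the arms differ.

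**Working it through.** **Inputs from the documents.** Number of primary scores k = 3 or 5 (Section 5); 0.05 per test (Section 8); 12 infants per arm and effect size 1.09 (Section 8).

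**Assumptions.** Two-sided tests, one between-arm test per score, and an equal correlation r between every pair of test statistics. The documents give no correlation, so a range is shown. For power, 1.09 is treated as a between-arm standardised mean difference, which Section 8 does not state.

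**The plan's own figure.** With d = 1.09, two-sided 0.05 and 95% power, a two-sample t-test needs 23 per arm (19 if one-sided), not 12. The stated size is therefore not reproduced as a two-arm calculation. That is a separate issue, and nothing below on false-positive rates depends on it.

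**Step 1: any one positive score counts, independent scores.** Error = 1 − (1 − 0.05)^k.
- k = 5: 1 − 0.95^5 = 0.226.
- k = 3: 1 − 0.95^3 = 0.143.

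**Step 2: correlated scores.** Write each test statistic as √r·U + √(1−r)·e, with U and e standard normal. Given U = u, a score is non-significant with probability a(u) = Φ((1.96 − √r·u)/√(1−r)) − Φ((−1.96 − √r·u)/√(1−r)). With φ the standard normal density, integrating numerically over u:
- any-one error = 1 − ∫ a(u)^k φ(u) du
- all-pass error with no true effect on any score = ∫ (1 − a(u))^k φ(u) du

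| r | Any of 5 | Any of 3 | All 5 | All 3 |
|---|---|---|---|---|
| 0 | 22.6% | 14.3% | <0.01% | 0.01% |
| 0.5 | 18.3% | 12.5% | 0.1% | 0.3% |
| 0.8 | 12.7% | 9.8% | 0.8% | 1.4% |
| 0.9 | 10.2% | 8.4% | 1.7% | 2.3% |

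At r = 0.99 the any-one rates fall to about 6% for both five and three scores, and the all-pass rate for three scores rises to 4.0%.

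**Step 3: worst case when all must pass.** If at least one score has no true effect, all scores can pass only if that one is falsely positive, so the error cannot exceed 5%. It approaches that bound when the other scores differ strongly (4.4% with exact Mann-Whitney at 12 per arm). The last two columns above assume no effect on any score, so they are not the worst case.

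**Step 4: separate claims.** If each score supports only its own claim, the error is 5% per score.

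**Step 5: check with a realistic test.** Exact Mann-Whitney U at 12 per arm has true size 4.49% because it is discrete. By simulation over r = 0 to 0.9, the any-one rate is 20.4% to 10.0% for five scores and 12.8% to 8.1% for three. With Holm, every case is at or below 4.3%.

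**Step 6: power per score.** Holm's first step for five scores is 0.05/5 = 0.01. Exact Mann-Whitney with d = 1.09 and 12 per arm has power of about 68% at 0.05 and 41% at 0.01.

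**The case against.** A reader might infer that familywise error is simply uncontrolled, at 10% to 23%. The documents do not support that. Nowhere do they say that one positive score means success; the any-one rule is only one of the rules they leave open. Sections 2 and 5 list the instruments as separate items, which also fits one claim per instrument at 5% each. An all-must-pass rule would need no adjustment. This objection stands: what can be shown is that the rule is missing.

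The rates also describe between-arm tests that the plan does not contain. The missing test is the more basic gap, and the multiplicity question follows from it. The correlation range is a choice: stopping at 0.9 sets the lower end, and higher values bring the rate close to 5%. In the other direction, weeks 4, 8 and 12 are not counted and could raise it. The percentages are therefore illustrations, not bounds.

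It could further be said that a 24-infant trial is exploratory and needs no familywise control. That carries less weight: the plan labels these outcomes primary, states 95% power at α = 0.05 and does not call itself exploratory. Naming a between-arm test alone would still leave three to five unadjusted primary tests with no rule for reading them together.

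**Conclusion.** The point holds as a missing specification: the plan names neither the between-arm test nor the success rule, so the false-positive rate of its primary conclusion cannot be stated. Depending on the rule eventually used, that rate could be at most 5% (all must pass), 5% per claim (separate claims), or about 23% to 10% for five scores and 14% to 8% for three (any one positive, assumed r from 0 to 0.9). The any-one figures assume two-sided 0.05 tests, equal correlations and no true effect on any score.

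Two readings go too far. One is that the plan has adopted an any-one rule; it has adopted none. The other is that an all-must-pass rule has an error of only about 2%; that figure requires no effect on any score and r no higher than 0.9, and the correct bound is 5%.

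**What to change.** 1. **Section 8, first:** name one between-arm test per primary score at week 12, for example a two-sided exact Mann-Whitney U on change from baseline. Label the within-arm Wilcoxon tests and the week 4 and week 8 results descriptive.
2. **If no outcome data have been examined,** choose one of two rules. Either name one primary score in Section 5, tested at 0.05, and make the others secondary with effect estimates and 95% confidence intervals; or keep all five scores (Bayley III counted as three), apply Holm at familywise 0.05, and claim an effect only for scores that pass.
3. **If outcome data have been seen,** apply Holm to all five and report the test, time point and rule as chosen post hoc. Holm then limits selective reporting but does not restore confirmatory status. Parts of the document are in the past tense, which does not by itself settle which case applies; the sponsor should say.
4. **Reconcile Section 2 with Section 5.** This is substantive, because it decides which scores are confirmatory.

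**Cost.** Text edits to Sections 2, 5 and 8, with no new visits or measurements. A single primary score gives up confirmatory claims on the rest. Holm lowers power per score: on the assumptions above, about 41% at its first step against 68% at 0.05. If all five scores truly differ by 1.09 (r = 0.5 assumed), Holm finds at least one in about 78% of trials and a given score in about 51%; if only one differs, it is found in about 41%. An all-must-pass rule is also valid without adjustment, but with all five scores differing by 1.09 it succeeds in only about 32%. The shortfall of these powers against the stated 95% is a separate sample-size issue.

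### The 0.95 power in Section 8 does not apply to the randomised comparison: 12 infants per arm give about 0.72 even if the true between-arm effect is 1.09 SD

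*Combined protocol and SAP*

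**What the plan says.** The Sample Size Calculation in Section 8 opens "Based on a similar study" and reports that "the effect size was calculated as 1.09". With G*Power it arrives at 24 infants, 12 in each group, a size that "was determined for α =0.05 and power=0.95". It does not state the effect index, outcome, time point, contrast, test or sidedness.

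Four other places bear on what that power refers to:

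- The background text just before Section 2 says: "No previous study has been found in which family education of risky babies was followed up with telerehabilitation".
- Section 3 (Groups) trains families in the clinic in both arms. One arm then has weekly video sessions and calls on two days a week. In the other, "Families received a single session of exercise training in the clinic and were asked to continue the exercises independently".
- Section 6 gives the home prescription once, with no distinction by arm: "Families instructed to perform exercises for 30-45 minutes, 3 days per week, for 12 weeks".
- Section 5 lists HINE, Bayley III and GAS as primary outcomes. Section 8 (Statistical Methods) gives these scores only a pre/post Wilcoxon signed-ranks test, and assigns Mann-Whitney U and chi-square to demographic data.

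**The concern.** A reader of Section 8 will take 0.95 as the chance that this trial detects a benefit of telerehabilitation follow-up, because that is what is randomised and because secondary objective 1 compares the two groups. The figure looks too high for 12 against 12, even with an effect as large as 1.09 SD.

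The input also lacks support. The authors report finding no direct precedent, the arms differ in follow-up rather than in whether families are taught exercises, and 1.09 is linked to none of the three primary measures. If the true increment is smaller than 1.09 SD, power falls further.

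What is at stake is how a null result is read. A trial described as having 0.95 power invites the conclusion that remote follow-up adds nothing, when the comparison may have had little chance of showing a moderate benefit.

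**Working it through.** **Inputs.** From Section 8: effect size 1.09, alpha 0.05, target power 0.95, n = 12 per group. Not stated, so assumed: 1.09 is a standardised mean difference d (SD = 1), and there is no dropout. Sidedness is tried both ways.

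**1. Trying to reproduce 12 per group as a two-group comparison.**

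Normal approximation, two-sided: n per arm = 2(z₀.₉₇₅ + z₀.₉₅)²/d² = 2(1.960 + 1.645)²/1.09² = 21.9, so 22.

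Noncentral t: noncentrality = d√(n/2), with 2n − 2 degrees of freedom. For Mann-Whitney U, n is multiplied by the asymptotic relative efficiency 3/π ≈ 0.955.

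| Test at d = 1.09 | n per arm for 0.95 | Power at 12 per arm |
|---|---|---|
| t, two-sided | 23 | 0.72 |
| Mann-Whitney, two-sided | 24 | 0.70 |
| t, one-sided | 19 | 0.83 |
| Mann-Whitney, one-sided | 20 | 0.81 |

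For the first row at n = 12: noncentrality = 1.09 × √6 = 2.67, df = 22, critical t = 2.074, power = 0.723. At n = 22 per arm power is 0.942, and at n = 23 it is 0.951. None of these variants gives 12 per group, and the total needed is 38 to 48 against the stated 24.

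**2. What does come close to 12.** For a within-group pre/post test, noncentrality = d√n, with n multiplied by 3/π for the signed-rank test.

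- Signed-rank, one-sided: n = 11 gives 0.948 and n = 12 gives 0.963, so 12 is the smallest n that reaches 0.95.
- Paired t, one-sided: n = 11.
- Two-sided: n = 14 for either test. At n = 12, power is 0.915 (signed-rank) or 0.929 (paired t).

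The signed-rank test is also the one Section 8 names for the outcome scores. The match suggests a pre/post calculation but does not establish one, because test and sidedness are not stated.

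**3. Other readings.**

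- If 1.09 were Cohen's f in a two-group ANOVA, about 14 infants in total would be enough, so 24 is not reproduced.
- A repeated-measures ANOVA with f = 1.09/2 = 0.545 and 24 infants reaches 0.95 or more under some correlation assumptions. For example, the between-group test with two measurements and correlation 0 gives 0.950, while correlation 0.5 gives 0.838. The group-by-time test gives 0.950 or more at every correlation tried (0 to 0.75). Section 8 plans no such analysis and states no correlation.

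**4. What 12 per arm can detect** (two-sided t, alpha 0.05). Solving for d gives 1.20 SD at 80% power and 1.54 SD at 95% power. At smaller effects, which are assumed because the documents give none:

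| Assumed d | Power at 12 per arm | n per arm for 0.95 |
|---|---|---|
| 0.8 | 0.47 | 42 |
| 0.5 | 0.22 | 105 |
| 0.3 | 0.11 | 290 |

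**The case against.** The strongest defence is that a borrowed effect size is a planning assumption. Where no direct precedent has been found, taking a figure from a similar study is ordinary practice. The other arm has one session and no further contact for 12 weeks, so adherence and exercise quality could diverge enough to make a large increment possible. The primary objective is worded as evaluating the approach, with the group comparison listed as secondary, so 0.95 may have been meant for a pre/post question. The powers at 0.3 to 0.8 SD rest on effects chosen for illustration.

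Much of this stands. A reader might infer that 1.09 cannot describe this contrast, or that the input is simply wrong. The documents do not support that. The background says such a study was not found, not that none exists, and Section 8 does not say what the similar study compared. Nor can one infer that the increment must be small because both arms exercise: Section 6 records what families were instructed to do, not what they did.

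None of it rescues 0.95 for the between-arm comparison, because the shortfall to 0.72 appears with 1.09 taken at face value. If 0.95 does belong to a pre/post test, it is not the power of the randomised contrast. Infants develop over 12 weeks in either arm, so a within-group change does not measure what follow-up adds.

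**Conclusion.** The point holds. For telerehabilitation against single-session education, 12 infants per arm give about 0.72 power at 1.09 SD (two-sided t-test, alpha 0.05), 0.70 with Mann-Whitney U, and 0.83 with a one-sided t-test. Reaching 0.95 would take about 23 per arm (46 in total). These figures assume that 1.09 is a standardised mean difference, that each infant contributes one outcome value to a two-group test, and that none are lost.

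That 1.09 may be optimistic is a secondary point and a judgement: its outcome and contrast are missing, so its relevance is unjustified rather than disproved. That the calculation was a pre/post one is an inference from the match at n = 12. The powers below 1.09 SD are illustrations and not predictions.

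**What to change.** Keep 24 infants and revise Section 8 as follows.

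1. Replace the 0.95 with the between-arm figures for 12 per arm: about 0.72 power at 1.09 SD, and detectable effects of 1.20 SD at 80% power and 1.54 SD at 95% power (two-sided t, alpha 0.05).
2. Give power at smaller effects, labelled as illustrative assumptions: 0.47 at 0.8 SD and 0.22 at 0.5 SD.
3. Name the one primary outcome the calculation refers to, and add a between-arm test of it, for example Mann-Whitney U on the change score (power about 0.70 at 1.09 SD). Without this, Section 8 would quote power for an analysis it does not contain.
4. State what 1.09 measured in the source study: outcome, comparator, effect index, and whether it was a between-group or a pre/post effect.
5. State that the trial can reliably detect only large between-arm effects, so a null result is not evidence of no benefit.

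The cost is SAP text and one added between-arm test, with no extra infants and no change to the intervention. The downside is a less favourable power statement. Expressing the detectable effect in score points would also need an SD for the chosen outcome, which the documents do not give.

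### The stated 0.95 power does not hold for the two-arm comparison: 12 infants per group at effect size 1.09 give about 0.70 to 0.72

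*Combined protocol and SAP*

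**What the plan says.** Section 8, Sample Size Calculation, says that from a similar published study "the effect size was calculated as 1.09", and that with G*Power "a total sample size of 24 infants (12 per group) was determined" for "α =0.05 and power=0.95". It does not give the test, the sidedness, the effect-size metric, the outcome behind 1.09 or an allowance for dropout.

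Section 3 describes the study as "A prospective, randomized, controlled trial conducted at the Risky Infants Polyclinic", with a telerehabilitation group and a single-session education group. The first secondary objective in Section 2 is to "Compare the motor, cognitive, and language developmental progress of infants in telerehabilitation and single-session education groups".

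Under Statistical Methods, Section 8 assigns Mann-Whitney and chi-square tests to demographic data and the Wilcoxon signed-rank test to before-after change in Bayley III, HINE and GAS. It names no between-arm test for an outcome.

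**The concern.** The sample size is given per group in a two-arm randomized trial that sets out to compare the arms, so a reader will take 0.95 as the power of that comparison. Twelve per group is far too few for 0.95 power at a standardized difference of 1.09.

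The figure matters most if the result is not significant. Read against 95% power, it looks like good evidence that weekly telerehabilitation adds nothing to a single training session. At the true power it is inconclusive.

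**Working it through.** **Inputs from the documents.** Effect size 1.09, alpha 0.05, target power 0.95, 12 per group (Section 8); two randomized arms (Section 3).

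**Assumptions where the plan is silent.** 1.09 is a standardized mean difference d (SD = 1); the test is two-sided, with one-sided also shown; there is no dropout.

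**1. Two-sample t-test, n = 12 per group.** Power is the upper tail of the noncentral t distribution with df = 2n − 2 and noncentrality d√(n/2), beyond the critical value.
- Noncentrality = 1.09 × √(12/2) = 1.09 × 2.449 = 2.67; df = 22; two-sided critical value 2.074.
- Power = **0.723**, so the type II error is 1 − 0.723 = 0.277.

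**2. Mann-Whitney test.** The same formula applies, with n multiplied by the asymptotic relative efficiency for normal data, 3/π = 0.955.
- Effective n = 12 × 0.955 = 11.46; noncentrality = 1.09 × √(11.46/2) = 2.61; df = 20.9.
- Power = **0.701**, so the type II error is 0.299. A simulation of 20,000 trials gave 0.685.

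**3. Attempt to reproduce the plan's figure with a two-arm test.**

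| Test | Sides | Power at 12 per group | n per group for 0.95 | Total |
|---|---|---|---|---|
| t-test | 2 | 0.723 | 23 | 46 |
| Mann-Whitney (normal data) | 2 | 0.701 | 24 | 48 |
| t-test | 1 | 0.827 | 19 | 38 |
| Mann-Whitney (normal data) | 1 | 0.810 | 20 | 40 |

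Around the two-sided thresholds, the t-test has power 0.942 at 22 per group and 0.951 at 23. Mann-Whitney has 0.942 at 23 and 0.950 at 24. No row gives 12 per group.

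**4. Other readings of the inputs.**
- One-sided Mann-Whitney with heavy-tailed (Laplace) data: 0.941 at 12 per group; needs 13.
- 1.09 read as Cohen's f: total of 14, not 24.
- One-arm before-after signed-rank test, n = 12, with 1.09 as the standardized change: one-sided with normal data 0.963, needing exactly 12; two-sided with normal data 0.915, needing 14; two-sided with logistic data 0.952, needing exactly 12.

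The last reading can produce 12, but for change within a single arm.

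**5. What 12 per group can detect (two-sided).** For 0.95 power: d = 1.54 (t) or 1.58 (Mann-Whitney). For 0.80 power: d = 1.20 (t).

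**6. Dropout (assumption: two lost per arm, leaving 10).** Power at d = 1.09 falls to 0.635 (t) or 0.613 (Mann-Whitney).

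**The case against.** The strongest reply is that the plan never says 0.95 refers to the between-arm contrast. The only outcome test it names is the before-after signed-rank test. As shown above, that test needs exactly 12 under two settings: one-sided with normal data, or two-sided with logistic data. The calculation may then be correct for the wrong question, which would be a mismatch of design and test, not an arithmetic slip. Whether 1.09 is a between-arm or a within-arm effect cannot be settled from the documents.

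That stands as a possible explanation of where 12 came from. It does not rescue the figure. Before-after change in one arm is not the randomized comparison, and some developmental change over 12 weeks is to be expected in infants of either arm. If this was the calculation, the SAP still has to say that 0.95 does not apply to the difference between arms.

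A baseline-adjusted analysis would reach 0.946 at 12 per group if the baseline-outcome correlation were 0.7. Averaging repeated measures with low correlation could reach 0.95. The plan mentions neither analysis and gives no correlation.

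The total of 24 equals the two-sided Mann-Whitney requirement per group, so a per-group number may have been entered as a total. This is a guess, and the conclusion does not depend on it.

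One point in the reply stands in full: because the SAP names no between-arm outcome test, a corrected power statement needs such a test to refer to.

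**Conclusion.** The concern holds. At the plan's own effect size and alpha, 12 per group gives two-sided between-arm power of about 0.70 to 0.72, against a stated 0.95. The type II error is about 28 to 30%, between 5.5 (0.277/0.05) and 6 (0.299/0.05) times the implied 5%. Unstated sidedness does not close the gap, since one-sided power is 0.81 to 0.83.

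This rests on reading 1.09 as a standardized mean difference between arms, an unadjusted comparison, roughly normal data and no dropout. Losses would lower power further. The three primary outcomes in Section 5 have no multiplicity adjustment, and that is not reflected here either. The figure should be corrected before the plan is relied on.

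**What to change.** Keep 24 infants and replace the power statement in Section 8 with wording such as: *With 12 infants per group, a two-sided 0.05 comparison between groups has about 70 to 72% power for a standardized difference of 1.09; 95% power is available only for differences of about 1.54 to 1.58.* The higher figure in each range is the power of the t-test, and the lower end of the effect range is also the t-test; once the test is chosen, quote its own figures.

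In the same place:
- State the test, that it is two-sided and between-group, the metric of the 1.09, and the outcome it refers to.
- List that between-arm outcome test under Statistical Methods, so that the power describes a planned analysis.
- Say that a non-significant result will be described as inconclusive and reported with its confidence interval.
- If 12 came from a within-arm calculation, say so, and do not present 0.95 as power for the randomized comparison.

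The cost is SAP text and a less favourable stated power, with no extra infants. Keeping 0.95 at d = 1.09 would instead mean 46 infants (t-test) or 48 (Mann-Whitney).
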